There are very few studies of the possible clinical significance of vitamin D on the course of GS. In an unblinded study, 30 patients with GS, in addition to conventional anti-thyroid treatment with methimazole, were randomized to a daily supplement of 1.5 micrograms alfacalcidol or no alfacalcidol (33). After 24 weeks of treatment, the mean dose of methimazole was similar in the two groups. Treatment with alfacalcidol led to a significantly lower plasma concentration of total and free T3 and thyroxin (T4), while TSH was significantly higher in those who had received treatment with alfacalcidol. There was no difference in the plasma level of TRAb. Treatment with alfacalcidol led to a significant decrease in the plasma concentration of alkaline phosphatase (33). However, the clinical use of 1,25(OH)2D has been limited by hypercalcemic side effects. The fact that the activation of vitamin D from 25-hydroxyvitamin D to 1,25(OH)2D has now been shown to take place not only in the kidneys but also locally in a number of tissues, including the cells of the immune system, has increased interest in vitamin D's possible immunomodulatory properties (34). In an unpublished review of 90 medical charts from patients with GS treated at the Regional Hospital Silkeborg or the Department of Internal Medical and Endocrinology, Aarhus University

Hospital, a low plasma concentrations of 25OHD are associated with a significantly increased risk of recurrence of GS after cessation of anti-thyroid treatment. Compared to P-25OHD < 45nmol/l, a concentration > 45nmol/l was associated with a 60% reduced recurrence risk (RR 0.40; 95% CI, 0.22-0.71), while a P-25OHD concentration above compared to below 60 nmol/l was associated with a 21% (RR 0.79; 95% CI, 0.50-0.99) decreased recurrence risk. In contrast, there was no significant effect at a threshold value of 80 nmol/l (RR 1.08; 95%CI, 0.46 – 2.32). The study also showed a non-significantly reduced relapse risk in patients who used vitamin D supplements compared to those who did not take such a supplement (RR 0.71; 95%CI, 0.42 – 1.21). In the population, the overall recurrence rate was 47%.

The following describes the randomized study i).

The controlled cohort study ii) is described separately on page 18)

Purpose

To clarify the importance of vitamin D for the course of GS, as we want to test the following hypotheses:

Primary hypothesis.

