The hospital pharmacy, Aarhus University Hospital, will carry out block-randomization, so that for every 4-16 participants included, there will be an equal number in each of those treated with either placebo or vitamin D supplementation. The exact size of the blocks will be unknown to the investigator. The participants are allocated consecutively. Site-randomization will be used to ensure equal randomization of study subjects at each participating department.

For each randomization number, the pharmacy supplies an opaque, sealed envelope numbered with the study's randomization number. The envelope can be opened if there is an urgent need to obtain information about which study medication the participant in question is receiving, as the envelope contains information about the contents of the tablets that the subject is taking. In this case, this is noted in the CRF, including the reason why the randomization code for the patient in question has been broken. The envelopes will be stored at Aarhus University Hospital.

The hospital pharmacy keeps a randomization list indicating the treatment group for all randomization numbers. The license is handed over to the Investigator when the experiment has been completed.

Data collection

The studies are carried out as outlined in Figure 1.

Baseline information, randomization and initiation of project medicine must begin within three months of anti-thyroid drug treatment.

For a sub-cohort of 100 patients (the first 100 subjects recruited from the outpatient clinics at the Medical Endocrinology Department, Aarhus University Hospital as well as interested participants from the regional hospitals in the central region) baseline information and the study program will be collected within four weeks after diagnosis of GS. Randomization and start-up of the project medication will take place immediately afterwards for this group.

In accordance with section 43, subsection 1 of the Health Act, participants' consent will be obtained to, via the medical charts, to collect information about treatment choice and course of GS, duration of treatment, occurrence of complications and side effects, including Graves' orbitopathy, side effects to the anti-thyroid treatment, as well as information about infections, other medical treatment, new illnesses including contact with a doctor and admissions.

Baseline

Based on medical record information, interview and questionnaire, the following will be registered in the CRF:

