The study was created on the initiative of doctors from the Department of Medical Endocrinology, Aarhus University Hospital. No one from the project group has financial interests in the study.

Expenses for the investigation will be financed by the departments involved, as fund support is also applied for.

No financial remuneration is provided to the test subjects, but possibly a transport allowance.

Study medication in the form of vitamin D and placebo is provided free of charge by the food manufacturer and dietary supplement manufacturer Orkla Health.

Figure 1. Flow-chart showing the course of treatment and investigations in the individual participants (n=260) randomized to treatment with vitamin D or similar placebo.

*In a sub-cohort of 100 participants additional measurement will be performed in terms of: blood pressure, pulse wave velocity (arterial stiffness), muscle- and balance-measurements, bone mineral density (BMD) and body composition (by DXA-scans), 3D bone microstructure (by HR pQCT- scans), and immunological analysis. From this sub-cohort 30 participants will undertake muscle and fat biopsy at baseline, 3 and 9 months.

Statistical analysis plan, final

Analyses of treatment effects will be based on the intention-to-treat principle. The first analysis will compare baseline characteristics by randomized treatment assignment to ensure that balance was achieved by the randomization. Characteristics to be examined include known risk factors for treatment failure including age, sex, smoking habits, severity of thyrotoxicosis, former use of vitamin D and baseline vitamin D status.

Differences between groups will be evaluated using a Chi Square test for categorical variables and a two-sample *t* test or Wilcoxon ranksum test, as appropriate, for continuous variables. For the primary outcome, the risk of treatment failure will be calculated as risk ratio (RR) with 95% confidence interval (CI).

With the intention-to-treat (ITT) approach, all subject who had been randomized and had received at least one dose of study medication will be included in the analysis. If study outcome is unknown, e.g. study withdrawal or exclusion, participants will be included in the ITT assuming either a *worst-case scenario* (all had treatment failure) or a *best-case scenario* (all experienced a treatment success)

In per-protocol analyses, only participants in whom outcomes can be assessed will be included.

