In a sub-analysis, the risk of relapse at any given time after ATD discontinuation until 12 ± 1 months will be examined using Cox regression.

In pre-specified analyses, the interaction between the intervention and baseline 25(OH)D status (insufficient (<50 mmol/L) or replete) and prior use of vitamin D supplementation (yes or no) will be assessed using logistic regression.

In addition to the original SAP, we will explore the interaction between the intervention and risk factors for relapse such as sex, age (above or below 40 year), time since diagnosis (above or below 35 days), and smoking status (current vs not). In case of significant interaction, the effect of intervention will be tested in each group separately.

References

(8) Engel AG. Neuromuscular manifestations of Graves' disease. *Mayo Clin Proc* 1972 Dec;47(12):919-925.

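### Optional gain, not an error: the primary risk ratio is planned without site or baseline covariates, though allocation is by site and the SAP lists six predictors of failure

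*Combined protocol and SAP*

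**What the plan says.** Under *Statistical analysis plan, final*, the primary estimate is described in one sentence: "For the primary outcome, the risk of treatment failure will be calculated as risk ratio (RR) with 95% confidence interval (CI". Group differences in categorical variables are to be tested by chi-square, and continuous variables by a two-sample t test or rank-sum test. *Statistical analysis plan (Original)* likewise names Fisher's exact or chi-square, and a t test or non-parametric equivalent for other measures. Neither plan names a covariate or a site term for these comparisons.

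Allocation is in blocks, and under *Procedures for randomization*: "Site-randomization will be used to ensure equal randomization of study subjects at each participating department".

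The final SAP opens with a baseline comparison: "The first analysis will compare baseline characteristics by randomized treatment assignment to ensure that balance was achieved by the randomization". The variables are then listed: "Characteristics to be examined include known risk factors for treatment failure including age, sex, smoking habits, severity of thyrotoxicosis", together with "former use of vitamin D and baseline vitamin D status". That makes six. Five of them return in interaction analyses: "baseline 25(OH)D status (insufficient (<50 mmol/L) or replete) and prior use of vitamin D supplementation (yes or no", and later "we will explore the interaction between the intervention and risk factors for relapse such as sex, age (above or below 40 year", followed by time since diagnosis and smoking. Severity does not return. None of the six enters the main effect estimate, and no sentence says what follows if the baseline comparison shows a difference.

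**The concern.** The plan sets N = 260 for 80% power and does not inflate it for drop-out; it relies on replacement until the end of 2017. Adjusting for baseline values that are collected anyway can raise power at the same N, if those values predict failure well enough. It also brings the analysis into line with the site-based allocation.

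The open sentence on balance is a smaller matter. If each of six independent baseline comparisons were tested at 0.05, at least one would be significant by chance in 1 - 0.95^6 = 26.5% of trials. Saying in advance that such a result changes nothing removes any later debate.

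The same efficiency question applies to continuous secondary outcomes measured at baseline and follow-up. Two-sample tests on follow-up values make no use of the baseline measurement. Only weight is described as a change under *Secondary outcome measures*.

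**Working it through.** **1. The plan's own figure.** Inputs from *Population size*: 50% v 33%, alpha 0.05 (two-sided assumed), power 80%, 1:1. Pooled-variance formula, no continuity correction:

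n per arm = [1.96·√(2·0.415·0.585) + 0.8416·√(0.50·0.50 + 0.33·0.67)]² / 0.17² = 130.7, so 131 per arm and 262 in total. Power at 130 per arm is 79.8%. The stated 260 reproduces.

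**2. Simulation set-up.** The main run has 10,000 trials per setting; further runs have 3,000 to 4,000. All use N = 260, marginal risks 0.50 and 0.33, and 1:1 blocks within site. The main run assumes seven sites (104, 39, 31, 26, 23, 19, 18; the last two pooled), site SD 0.2 on the logit scale, 20/80 sex split, 30/70 smoking, 40% low 25OHD and 40% prior use. Other runs use 2, 6 or 10 sites. Crude: chi-square or Wald test of log RR. Adjusted: logistic model with site and six factors, standardised to a marginal RR, robust SE with an n-k correction.

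**3. Power difference, adjusted minus crude (points; crude about 80%), six factors equally predictive.**

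| Joint AUC | Main run | Further runs |
|---|---|---|
| 0.50 | -2.3 | -1.1 to -2.2 |
| 0.62 | not run | -0.3 to +0.2 |
| 0.65 | +0.2 | +0.7 to +1.9 |
| 0.68-0.69 | +2.6 | +2.5 to +3.7 |
| 0.73 | +5.0 | +4.2 to +5.7 |
| 0.78 | +7.4 | +7.7 |

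Break-even is near AUC 0.62. Reaching 0.73 needs every factor to be informative: odds ratios of about 2.6 for sex, 2.3 for smoking, 2.2 each for 25OHD and prior use, and 1.46 per SD for age and severity. If only smoking and severity predict, at 0.30, 0.38 or 0.48 per SD, the differences are -0.1, +0.7 and +2.3.

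**4. Arithmetic cross-check.** Power of 79.8% corresponds to a standardised effect of 1.96 + 0.834 = 2.794. The mean SE of log RR falls by 7% at AUC 0.73: 2.794/0.93 = 3.004, and Φ(3.004 - 1.96) = 85.2%, or +5.4 points. At AUC 0.78 it falls by 10%: 2.794/0.90 = 3.104, giving 87.4%, or +7.6. Both agree with the table.

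**5. The variance correction matters.** Without n-k, the difference is -0.6 to +0.1 points at AUC 0.50 and +4.9 to +7.0 at 0.73. The stated loss of 1 to 2 points therefore belongs to the corrected SE.

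**6. What the documents say about predictive strength.** The *D vitamin* background section reports relapse in 90 charts: "Compared to P-25OHD < 45nmol/l, a concentration > 45nmol/l was associated with a 60% reduced recurrence risk (RR 0.40; 95% CI, 0.22-0.71". The RR is 0.79 at 60 nmol/l and 1.08 at 80 nmol/l. Supplement use has RR 0.71 (0.42-1.21). Let 25OHD be the only predictor, with share p = 0.40 low and placebo risk 0.50: risk in the low group = 0.5/(p + RR(1-p)). At RR 0.40 this is 0.5/0.64 = 0.781, against 0.313 in the rest.

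| RR for 25OHD | 0.40 | 0.60 | 0.71 | 0.79 |
|---|---|---|---|---|
| Predicts in both arms | +6.4 | +0.9 | -0.8 | -1.4 |
| Predicts under placebo only | -0.6 | -1.5 | -2.0 | -1.7 |

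Here 0.40 and 0.79 are chart estimates, 0.71 is the upper confidence limit at the 45 nmol/l cut, and 0.60 is an assumed midpoint. The lower row is what would follow if the supplement corrects the deficit.

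**7. Unknown outcomes.** With 10% unknown at random, the differences at AUC 0.50, 0.73 and 0.78 are -3.0, +2.6 and +5.6 if all are set to failure, and -2.1, +4.5 and +6.1 if set to success.

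**8. Type I error (main run).** Crude 4.9-5.5%; adjusted 4.6-5.0%. Taking the smaller p of the crude and full models gives 5.7-7.2%, so one of them must be named primary.

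**9. Continuous outcomes.** With baseline-to-follow-up correlation r, ANCOVA saves r² of the variance against raw follow-up values and (1-r)/2 against change scores. At assumed r = 0.5, 0.7, 0.9 this is 25, 49, 81% and 25, 15, 5%.

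**The case against.** The strongest reply is that nothing is broken. The crude RR and chi-square match the sample-size basis, hold their error rate, and are simple to report. Even the sign of the benefit depends on prognostic strength that the documents do not give. The only evidence is 90 charts on relapse, while the primary endpoint also counts radioiodine referral, surgery and failure to taper. The SAP itself tests an interaction with 25OHD, so the placebo-only case in which adjustment loses power is not remote. All of this stands, and it is why the point is optional.

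Several practical limits stand too. Site numbers and sizes are not given. Table 2 (May 11, 2017) gives replacements the drop-out's allocation, and drop-outs who took a dose stay in the ITT set, so blocks are not fully intact and the analysed number may exceed 260. Entry requires raised T3 and/or T4, so T3 at diagnosis may be incomplete. The SAP's list of factors is introduced as examples, so fixing it at six is a choice.

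What does not stand is that this is mere taste. At moderate to good predictive strength the gain is several points at almost no cost, and the RR stays marginal, so the quantity estimated does not change.

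A reader might infer that the missing sentence on imbalance lets the sponsor choose between results. The documents do not support that. No adjusted primary analysis is planned and no p-value rule for imbalance is given, so on a plain reading the crude result counts.

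**Conclusion.** The point holds as an inexpensive improvement. Adjustment for site and the six factors changes power by about -1 to -2 points if they are uninformative (up to -3 with 10% unknown outcomes set to failure), about 0 to +2 at a joint AUC of 0.62 to 0.65, and about +4 to +5 at 0.73. If 25OHD alone predicts, and only under placebo, the loss is about 1 to 2 points. These figures rest on assumed AUCs, site sizes and intact blocks.

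Two stronger readings should be resisted. One is that ignoring site and covariates makes the primary analysis invalid: simulated crude type I error is close to 5%. The other is that adjustment will deliver 5 points: that needs all six factors to be informative, and the chart review makes a gain plausible without establishing it. The chart RRs also fade as the cut rises, which argues against a linear 25OHD term.

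**What to change.** If the data are still blinded, amend the final SAP as follows.

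- **Primary result:** marginal RR with 95% CI from logistic regression with standardisation and a robust SE with n-k correction.
- **Covariates:** site (sites with fewer than 20 randomised pooled; a single such site joins the next smallest); age, continuous; sex; current smoking; severity as T3 at diagnosis, or T4 where T3 is missing, as a multiple of the assay's upper limit on the log scale; baseline 25OHD at the SAP's cut of 50 (the final SAP prints mmol/L, the background nmol/l, so the unit must be confirmed); former vitamin D use.
- **Missing covariates:** median or commonest category over both arms together, with an indicator if more than 5% are missing.
- **Failed fit:** pool sites further before dropping them.
- **Unknown outcomes:** apply the same model to the worst-case and best-case ITT sets.
- **Baseline comparison:** state that its results do not change the model.
- **Supportive:** crude RR and chi-square.

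The final SAP carries no date, completion was expected in 2021 and the translation is dated August 2022. If unblinding has occurred, keep the crude RR primary and label the adjusted RR supportive.

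For continuous secondary outcomes measured at baseline and follow-up, replace the two-sample tests with ANCOVA on the baseline value.

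The cost is SAP wording, a little programming, some work to put assays on a common scale, and about 1 to 2 points of power if the factors prove uninformative.

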Treatment with vitamin D supplementation will reduce the number of treatment failure of Graves' disease in the intervention group by 33% compared to the placebo group.

Secondary hypotheses.

Treatment with vitamin D supplements will accelerate the normalization of bone turnover and muscle balance function and shorten the time to symptom freedom.

Vitamin D supplementation reduces vascular stiffness in patients with GS.

Design

The study is conducted as a double-blind, randomized and placebo-controlled trial with a clinical follow-up time of up to three years. The participants are patients with newly diagnosed Graves' disease recruited from the hospitals in the Central Denmark Region. The study proceeds with two parallel study groups. The participants in each of the study groups take 1 tablet daily. Each tablet is either placebo or 70 micrograms of cholecalciferol. The placebo and cholecalciferol tablets are identical in appearance.

All subjects are randomized to one of the following two groups:

Group 1: 1 placebo tablet daily (50% of participants)

Group 2: 1 tablet of cholecalciferol of 70 micrograms (50% of the participants)

The study proceeds as shown in Figure 1.

After randomisation, a smaller cohort will also undergo a study program as outlined below.

Register-based follow-up studies will be carried out after 5 and 10 years on the entire cohort.

When 260 subjects have been randomized, drop-outs will be replaced until the end of 2017 when the inclusion period ends. Study closure is when the last participant has completed the study program as described in figure 1, alternatively has stopped participation in the study.

The individual participant stops taking the project medication at the latest 12 months +/- 1 month after the end of anti-thyroid treatment - possibly earlier (cf. section on withdrawal). For the individual participant, the maximum length of treatment will be 36 months.

A control cohort of 55 healthy sex- and age-matched individuals is established.

Primary outcome measures:

The primary effect measure is assessed based on whether the participants have benefited from the treatment as assessed by:

- Treatment success: No signs of hyperthyroidism 12±1 months after the end of anti-thyroid treatment. Criteria for treatment failure not met.

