Other effect measures are calculated with t-test for two independent groups or a corresponding non-parametric test, depending on the distribution of the material. A significance level of 0.05 will be used. Primarily, data will be analyzed according to the "intention-to-treat" principle, although secondarily an "on treatment" analysis will be carried out, where the degree of compliance is corrected.

The intention-to-treat population consists of all participants who have been randomized to the study and who have received at least one dose of the study medication. In the event of missing data in the Intention-to-treat analysis, "last value carried forward" will be used. In the final protocol, there will be an account of unused or omission of inauthentic data, as well as an account of reasons for any deviations from the originally planned statistical analyses.

It is planned to carry out interim analyzes when the sub-cohort of 100 subjects (which includes mainly from Aarhus University Hospital and Regional Hospital Silkeborg) has completed the entire study program. This is to ensure that this population can be included in a data analysis which will form the basis of a PhD thesis

Study population

260 patients, men and women, with newly diagnosed GS where anti-thyroid treatment is planned. Potential study participants are recruited from hospitals in Central Denmark Region in connection with patients' attendance at the outpatient clinic.

Inclusion criteria

- Newly diagnosed Graves' disease verified by TSH below the reference range and thyroxin and/or triiodothyronine (T3 and/or T4) above the upper reference range.
- Age 18 years or older
- Elevated plasma level of thyroid stimulating immunoglobulin (TRAb)

- Planned or started (< 3 months) medical anti-thyroid treatment
- Speaks and reads Danish.
- Written consent after oral and written information

Exclusion criteria

- Daily intake of vitamin D supplements of more than 10 micrograms, which the participant wishes to continue.
- A previously diagnose of hyperthyroidism
- Planned treatment with radioactive iodine or thyroidectomy
- Chronic granulomatous disease
- Significant hypercalcemia (ionized plasma calcium $> 1.40 \text{ mmol/l}$)
- Reduced kidney function (eGFR $< 45 \text{ ml/min}$)
- Regular intake of medication with known immuno-modulating effects, including systemic glucocorticoids ($>5\text{mg/day}$ for 3 months), imurel, methotrexate, TNF α -inhibiting agents.
- Active malignant disease

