- Alcohol abuse resulting in the need for treatment or hospitalization
- Lack of willingness or desire to participate in the study
- Abuse of euphoric substances
- Pregnancy at the time of inclusion

Patients who meet all inclusion criteria and none of the exclusion criteria will be invited to participate in the study.

Withdrawal

Participants will be asked to cease treatment with the project medicine when an exclusion criteria is met:

- Changed treatment strategy for hyperthyroidism (radioiodine therapy, surgery).
- Hypercalcemia or reduced kidney function
- Onset of diseases or initiation of medication intake as listed under exclusion criteria (except systemic glucocorticoid treatment due to thyroid-associated ophthalmopathy).
- Recurrence of hyperthyroidism after discontinuation of anti-thyroid treatment.

The investigator can stop the treatment for a participant if this is deemed necessary for the participant's safety.

In case of pregnancy, the participant can continue with the project medication. Participants in the intensively studied sub-cohort (n=100) will be excluded from further studies during pregnancy, due to the radiation risk associated with the scans. However, the participants can continue in the main study (n=260).

Population size

Vitamin D and relapse risk in Graves' disease

There are no previous human studies with treatment with vitamin D3 supplements. In a medical record review of 90 medical records from patients with GS treated at Region Hospital Silkeborg or Aarhus University Hospital, it was found that $P-25OHD > 45 \text{ nmol/L}$ was associated with a 60% reduced recurrence risk compared to $P-25OHD < 45 \text{ nmol/L}$ (RR 0.40, 95% CI 0.22–0.71). The study also showed a non-significantly reduced recurrence risk in patients who used vitamin D supplements compared to those who did not take such a supplement (RR 0.71; 95% CI 0.42-1.21). Power calculation: In order to show a difference in relapse risk for intervention with vitamin D compared to placebo of 33% (from 50% to 33%), a total of 260 participants must be included in the study, with 50% randomized to placebo and 50% to supplementation with vitamin D. ($\alpha=0.05$; $\beta=0.20$). Drop-outs will be replaced by the inclusion of new participants: Upon the inclusion of participant no. 260, drop-outs will be counted and replaced by the inclusion of new participant until the end of year 2017 when the Inclusion Period ends.

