Investigator allows direct access to source data/documents (including patient records) during monitoring, auditing and inspection from the Research Ethics Committee for Central Region and the GCP unit for Aarhus University Hospital and its partners. The participants are made aware of this and specific consent is obtained in the form of a power of attorney.

All information obtained will be handled in accordance with the Act on the Processing of Personal Data.

Research biobank

A research biobank will be set up where plasma taken from each subject will be stored at -80 degrees Celsius. The material will be analyzed as described under "biochemistry".

After the end of the experiment, remaining material will be transferred to a biobank, where it will be stored for up to 15 years before being destroyed. Participants will be asked to consent to this. The biobank will be notified to the Danish Data Protection Authority in accordance with applicable legislation.

Medicine accounting

The investigator will keep careful records of who the study medication has been delivered to, incl. date and amount of medicine dispensed. In addition, the amount of returned medication will be recorded. In each participant's CRF, the quantity, batch number, and date of dispensing of study medication are noted.

For each participant, treatment compliance will be calculated as the difference between the number of dispensed and returned doses. Regardless of degree of compliance, participants will be encouraged to continue in the trial. If a participant stops taking the project medicine during the course of the study, the time of cessation of taking the study medicine will be noted together with the reason why the participant has stopped taking the medicine. However, the participants will be asked to continue to come to planned control visits, which will improve the quality of subsequent intention-to-treat analyses.

Risks, side effects and inconvenience

Risks

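### The final SAP gives two unranked ITT versions of the primary result for unknown outcomes, and agreement between them does not show robustness

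*Combined protocol and SAP*

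**What the plan says.** The primary hypothesis (Purpose) is that vitamin D "will reduce the number of treatment failure of Graves' disease in the intervention group by 33% compared to the placebo group". The final SAP reports the primary outcome as an RR with 95% CI and bases treatment effects on intention to treat, meaning everyone randomised who took at least one dose. Those with unknown outcome are "included in the ITT assuming either a *worst-case scenario* (all had treatment failure) or a *best-case scenario* (all experienced a treatment success". The text does not separate the arms, so each version applies one value to both.

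Three other provisions bear on this:

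- The final SAP adds: "In per-protocol analyses, only participants in whom outcomes can be assessed will be included". That set is defined by having an outcome, not by adherence. It ranks below ITT, because the section opens by basing treatment effects on ITT.
- The Cox sub-analysis concerns "the risk of relapse at any given time after ATD discontinuation". It covers relapse only. The primary composite also includes radioiodine, surgery and failure to taper.
- The original SAP had a single rule, beginning "In the event of missing data in the Intention-to-treat analysis": last value carried forward. I treat it as superseded. If it still applied, it would be a third unranked version.

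Under Population size, "drop-outs will be counted and replaced by the inclusion of new participant until the end of year 2017". No drop-out rate is given anywhere.

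**The concern.** A primary analysis should produce one result that answers the primary hypothesis. Here the same data can give a significant RR in one ITT version and a non-significant RR in the other, and no rule covers that case. The decision could then be taken after the results are known.

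The second difficulty is what agreement would mean. A reader who sees a worst case and a best case that agree will tend to conclude that unknown outcomes cannot matter. The case least favourable to vitamin D has its unknowns fail while placebo unknowns succeed, and the most favourable case is the reverse. The plan runs neither.

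**Working it through.** **Inputs.** Population size gives 260 participants allocated 1:1 (130 per arm), failure 50% versus 33%, alpha 0.05 and power 80%. The proportions unknown (2%, 5%, 10%) are my assumptions.

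**1. The plan's own figure.** With two-sided alpha, pooled variance and no continuity correction:

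n = [1.96 √(2 × 0.415 × 0.585) + 0.84 √(0.5 × 0.5 + 0.33 × 0.67)]² / 0.17² ≈ 131 per arm, or 262 in total.

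This agrees with 260 to within rounding. Power at 130 per arm is 79.8%.

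**2. When the two versions are the extremes.** Let f be observed failures and m unknowns, with D for vitamin D, P for placebo and equal arm sizes.

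- All failure: RR = (f_D + m_D)/(f_P + m_P)
- All success: RR = f_D/f_P
- Largest possible: (f_D + m_D)/f_P
- Smallest possible: f_D/(f_P + m_P)

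With at least one observed failure per arm, the first two equal the last two only if m_D = 0 or m_P = 0. A grid of 3,969 configurations gave no exception.

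**3. Example with 13 unknown in each arm** (observed failures 39/117 on vitamin D and 58/117 on placebo; all 130 per arm in the denominator).

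| Assumption for unknowns | Failures D vs P | RR (95% CI) |
|---|---|---|
| All failure (plan) | 52 vs 71 | 0.73 (0.56–0.95) |
| All success (plan) | 39 vs 58 | 0.67 (0.49–0.93) |
| D fail, P succeed | 52 vs 58 | 0.90 (0.67–1.19) |
| D succeed, P fail | 39 vs 71 | 0.55 (0.40–0.75) |

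Both planned versions are significant and close together. The least favourable case is far from significance (p = 0.45).

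**4. The verdict can turn either way** (uncorrected chi-square).

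- Unknown 20 on D and 13 on P, observed 36/110 vs 58/117: all failure 56 vs 71, p = 0.063; all success 36 vs 58, p = 0.0045.
- Unknown 10 on D and 15 on P, observed 42/120 vs 57/115: all failure 52 vs 72, p = 0.013; all success 42 vs 57, p = 0.055.

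**5. How often they disagree.** One million simulated trials per setting, 130 per arm, binomial drop-out unrelated to outcome and equal in expectation, no replacement.

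| Unknown | Disagree (50% vs 33%) | Null rejection, both needed | Null rejection, either suffices |
|---|---|---|---|
| 2% | 6.6% | 4.1% | 6.8% |
| 5% | 11.1% | 3.3% | 7.5% |
| 10% | 16.8% | 2.5% | 8.2% |

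The null columns take 50% failure in both arms. One named version rejects in about 5.3% at 10% unknown. Power at 10% is 63% if both versions must be significant, 71–72% for one named version and 80% if either suffices.

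**6. With full replacement at 10%.** Each arm then has 130 known outcomes plus its dosed drop-outs, who remain in the ITT set. Disagreement falls to about 13%, and power for a named version is 75–78%.

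**7. Expected RR at 10% unknown.** All failure: (0.297 + 0.10)/(0.45 + 0.10) = 0.72. All success: 0.297/0.45 = 0.66, the planned effect.

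**The case against.** The best defence is that either/or means both versions will be reported and a claim made only if they agree. That would be conservative: 2.5% null rejection at 10% unknown. It is a reasonable reading, but the SAP does not state it, and it would cost power (63%). The commitments to explain deviations from the planned analyses (original SAP) and to publish positive, negative and inconclusive results (Publication) reduce the room for selection. They do not name the deciding analysis.

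Unknown outcomes may also be few. Radioiodine, surgery and failure to taper are known failures, chart data are collected, and of those who stop tablets, "the participants will be asked to continue to come to planned control visits". This stands, and it makes the low rates in the table the more relevant ones. For scale, corrected and uncorrected chi-square disagree in 3.8% of complete-data trials at the planned effect.

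Some stronger readings are not supported:

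- A reader might infer that the available-case set is also unranked. It is not; ITT comes first.
- A reader might infer that the SAP claims its scenarios bound the RR. It makes no such claim. The gap is in what their agreement can show.
- A reader might infer that a trivial imbalance settles the verdict. At 10% unknown, an imbalance of two gives disagreement in only about 9% of trials, and equal counts in under 1%.
- A reader might take 8.2% as the trial's error rate. That requires claiming success from whichever version is significant, which the plan does not propose.
- A reader might expect drop-out to differ by arm. The trial is double-blind with no side effects expected, so the documents give no reason for it.

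**Conclusion.** The point holds. The two ITT versions of the primary result are unranked, there is no rule for disagreement, and neither is the extreme case for the RR unless one arm has no unknowns. These follow from the text and do not depend on any drop-out rate.

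The size does depend on one. Under the stated assumptions, disagreement runs from about 7% of trials at 2% unknown to 17% at 10%, or 13% at 10% with full replacement. Actual replacement may be partial, since it ends with 2017, and 10% is illustrative, not an expectation drawn from the documents. If few outcomes are unknown, the effect is small.

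This should be fixed because it concerns the primary hypothesis and the remedy costs almost nothing. It does not show that the trial's result would be wrong.

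**What to change.** - Name one ITT analysis of all randomised and dosed participants as deciding the primary hypothesis. State that if the other version disagrees, the result is reported as not robust to unknown outcomes.
- Add the two arm-opposed scenarios (vitamin D unknowns fail and placebo unknowns succeed, and the reverse), or a tipping-point grid, as sensitivity analyses. Read them as limits, not as tests.
- Rename the 'per-protocol' set available-case, since it is selected on outcome availability.

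Multiple imputation within arm is an option, not a requirement. It relies on outcomes being missing at random, and without covariates it showed no power gain over available-case (75% versus 76% at 10% unknown).

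The cost is SAP wording, a little programming, and sensitivity limits visibly wider than the present pair. No new data or participants are needed. Naming one version does not make disagreement rarer; it settles beforehand which result counts.
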